4.2.3.2.2 Descriptive Analyses

Data will be summarized according to the assigned treatment sequence for both maintenance/escalation (Week 12-24) and response assessment/dose hold (Week 24-48) periods (see Table 4.10):

(1.i) Plac/120mg (x4), Q4/Hold

(1.j) Plac/120mg (x4), Q4/No Hold

(2a.i) 30mg (x4), Q4/No Esc/Hold

(2a.j) 30mg (x4), Q4/No Esc/No Hold

(3a.i) 60mg (x4), Q4/No Esc/Hold

(3a.j) 60mg (x4), Q4/No Esc/No Hold

(4.i) 120mg (x4), Q8/Hold

(4.j) 120mg (x4), Q8/No Hold

(5.i) 120mg (x4), Q4/Hold

(5.j) 120mg (x4), Q4/No Hold.

As treatment assignment is based on post-randomization efficacy results, only descriptive treatment summaries will be reported. No inferential analyses are planned. More specifically, the descriptive comparisons with exploratory nature will be made:

- between treatment group of subjects who had their dose hold from Week 24
- between treatment group of subjects who had not their dose hold from Week 24

in the MITT48 population who were initially randomized to any of the M1095 at Week 0 and who did not dose escalated.

Binary, continuous and time-to-event data will be reported in a way similar to the corresponding endpoints for the post-Week 12 exploratory analyses (refer to Sections 4.2.3.1.3, 4.2.3.1.4 and 4.2.3.1.5 for further information).

Planned Treatment Group and Dose Escalation/Hold	IGA = 0 at Week 24?	Treatment Label
		Response Assessment/Dose Hold Period (Week 24-52)
(1) - Placebo at Week 0, 1, 2, 3, 4, 6, 8 (and (1.i) M1095 120 mg at Week 12, 14, 16, 20 and dose hold from Week 24)	Yes	Plac/120mg (x4), Q4/Hold
(1.j) M1095 120 mg at Week 12, 14, 16 and Q4W	No	Plac/120mg (x4), Q4/No Hold
(6) - Secukinumab 300 mg at Week 0, 1, 2, 3, 4, 8 (and 12 and Q4W)	N/A	
(2) - M1095 30 mg at Week 0, 2, 4, 8 (and (2a.i) Q4W and dose hold from Week 24)	Yes	30mg (x4), Q4/No Esc/Hold
(2a.j) Q4W	No	30mg (x4), Q4/No Esc/No Hold
(2b) M1095 120 mg Q4W if escalation at Week 12)	N/A	
(3) - M1095 60 mg at Week 0, 2, 4, 8 (and (3a.i) Q4W and dose hold from Week 24)	Yes	60mg (x4), Q4/No Esc/Hold
(3a.j) Q4W	No	60mg (x4), Q4/No Esc/No Hold
(3b) M1095 120 mg Q4W if escalation at Week 12)	N/A	
(4) - M1095 120 mg at Week 0, 2, 4, 8 (and (4.i) 12 and Q8W)	Yes	120mg (x4), Q8/Hold
(4.j) 12 and Q8W and dose hold from Week 24)	No	120mg (x4), Q8/No Hold
(5) - M1095 120 mg Q2W at Week 0, 2, 4, 6, 8, 10 (5.i) 12 and Q4W and dose hold from Week 24)	Yes	120mg (x6), Q4/Hold
(5.j) 12 and Q4W	No	120mg (x6), Q4/No Hold

Note: The only treatment groups displayed in all exploratory analyses after M1095 dose hold/restart from Week 24 are the treatment groups identified by rows in white in the table. The other treatment groups identified by rows in gray are only displayed for completeness and information and will be presented in other tables. The descriptive comparisons will be made between treatment group of subjects who had their dose hold from Week 24 (in bold) and separately between treatment group of subjects who had no dose hold from Week 24.

Table 4.10: Planned Treatment Groups with Dose Escalation/Hold and their Labels for each Treatment Period for Exploratory Analyses after Week 24.

4.3 Quality of Life

All subjects in the ITT population will be selected for the analyses of Quality of Life (QoL) variables.

4.3.1 Variables

The QoL variables are:

- Change from baseline in Dermatology Life Quality Index (DLQI) total score and in DLQI subscales,
- Achievement of DLQI of 0 or 1 (binary variable),
- Change from baseline in the norm-based Short Form 36 (SF-36) scores for the eight sections and for the physical and mental summary components,
- Change from baseline in EuroQuality of Life Questionnaire for Psoriasis (EQ-PSO) as measured by VAS and EQ-PSO score for the 7 dimensions.

The derivations of QoL scores are described in the Appendices on page 68.

LOCF will be used to impute any missing values for the continuous variables and NRI for the binary variable (refer to Section 4.1.1.3).

4.3.2 Descriptive Analyses and Inferential Analyses

The raw continuous QoL variables at baseline and post-baseline visits as well as their change from baseline will be presented by randomized treatment group at each visit up to Week 48 using summary statistics, listings and appropriate graphical methods.

Treatment comparisons of continuous QoL variables will be assessed at all visits up to Week 12 by an ANCOVA including planned treatment group, actual prior biologic and weight stratum as factors and the baseline value as a covariate in the model. The treatment LSM, the corresponding SE and 95% CI and the pairwise LSM difference, the corresponding SE, 95% CI and p-value will be presented. This analysis will be replicated at Weeks 24, 36 and 48.

The proportions of the binary variable will be examined and reported as described in Section 4.2.2.2.1.

The analyses of QoL variables may be replicated using complete cases. Additional exploratory analyses of QoL may be performed.

4.4 Subject Demographics/Other Baseline Characteristics

The subject demographics and other baseline characteristics will be reported in the analysis populations specified in Table 4.11.

4.4.1 Variables

The variables are the demographics of subjects plus all data for background and other baseline characteristics such as relevant medical history, results of laboratory screens, drug tests and any other relevant information.

The demographics of subjects include:

- continuous age (in years) along with categorical age (< 45, ≥ 45 - < 65, ≥ 65), gender, race and ethnicity,
- country, geographical region (Europe, North America),
- height (in cm) at screening, continuous weight (in kg) as well as categorical weight (≤ 90 kg, > 90 kg) and Body Mass Index (BMI) (in kg/m²) at baseline. BMI will be calculated by dividing weight in kilograms by height in meters squared.
- randomized prior biologic use and weight stratum (as entered into IRT system by the sites).

Other baseline characteristics consist of:

- psoriasis medical history i.e. the number of significant flares of disease activity in the last 6 months, the time since diagnosis and the actual prior biologic use,
- results of laboratory screens, drug tests at baseline,
- IGA score, PASI score and percentage of BSA affected by psoriasis at baseline,
- DLQI total score, EQ-PSO total score (VAS), SF-36 physical and mental component summaries at baseline,
- PHQ-8 and eC-SSRS total score at baseline.

The variables of subject demographics and other baseline characteristics will be performed in the ITT population. Besides, these variables will be reported in other analysis populations to evaluate the differences between non-randomized treatment groups that are assigned on the basis of post-randomization efficacy results in the exploratory analyses after Week 12 and Week 24. All subjects within the ITT population and/or safety population will be included in the analysis of the results of laboratory screens, drug tests, PHQ-8 and eC-SSRS total score (refer to Table 4.11 for further details).

4.4.2 Descriptive Analyses

All data for background and demographic variables, psoriasis medical history, results of laboratory screens and drug tests, IGA score, PASI score and percentage of BSA as well as QoL and Patient Reported Outcomes (PRO) data will be summarized by treatment group as specified in Table 4.11 at screening and/or baseline visit. No treatment comparisons will be performed. This data will also be listed by treatment group and subject.

Table 4.11: Analysis Populations in Function of Demography Variables

Demography Variables	Analysis Population

 • Demographics • Psoriasis medical history • IGA score, PASI total score and percentage of BSA affected by psoriasis at baseline 	
 • ITT Population • MITT24 Population by assigned treatment sequence for both induction and maintenance/escalation periods. • MITT48 by assigned treatment sequence for both maintenance/escalation and response assessment/dose hold. • Week 12 IGA non-Responder Population by assigned treatment sequence for both induction and maintenance/escalation periods (optional)

 • DLQI total score, EQ-PSO total score, SF-36 physical and mental component summaries at baseline 	
 • ITT Population

 • Results of laboratory screens, drug tests at baseline, PHQ-8 and eC-SSRS total score at baseline 	
 • ITT Population/Safety Population

4.5 Analysis Populations

4.5.1 Variables

The analysis populations will be summarized in the enrolled population with the following variables:

- number and percentage of subjects who are enrolled but are not randomized overall and by reasons for exclusion,
- number and percentage of subjects who are:
 - randomized
 - in the ITT population,
 - in the MITT populations,
 - in the PP populations,
 - in the safety population.

4.5.2 Descriptive Analyses

The incidence in the various analysis populations will be presented by treatment group and overall if applicable for each treatment period. In addition, a listing of subjects excluded from

each analysis population with the primary reason for exclusion whenever available will be produced.

4.6 Subject Disposition

Subject disposition will be analyzed in the enrolled population unless stated otherwise.

4.6.1 Variables

Subject disposition will be described by:

- the number and percentages of subjects who are screened, randomized, treated, who completed the treatment period and/or study, who discontinued along with the primary reason for early discontinuation for the study overall as well as for each treatment period separately.
- the number and percentages of subjects who dose escalated from Week 12 or of subjects who had dose withheld from Week 24 for the maintenance/escalation period and the response assessment/dose hold period respectively.
- the number and percentage of subjects with important protocol deviations in the ITT population overall and grouped into categories for the study overall as well as for each treatment period separately,
- the number and percentages of subjects in analysis populations and excluded from the analysis populations,
- the time in weeks to study drug discontinuation due to any reasons and due to an AE for the induction period.

To assess the exploratory analyses after Week 12 and 24, the disposition of subjects after the post-randomization treatment assignment at Week 12 or Week 24 will be explored in the MITT24 or MITT48 populations and by assigned treatment sequence for the maintenance/escalation period or dose assessment/response hold period respectively using these variables:

- the number and percentage of subjects completing the maintenance/escalation period or dose assessment/response hold period,
- discontinuing the treatment during the maintenance/escalation period or dose assessment/response hold period and by primary discontinuation reason.

4.6.2 Descriptive Analyses

Subject disposition variables will be summarized by treatment group.

In addition, a listing of important protocol deviations will be presented by subject and treatment broken down by center.

4.6.3 Graphical Presentation

The time in weeks to study drug discontinuation due to any reasons and due to an AE will be represented graphically with Kaplan-Meier plots by treatment groups for the ITT population during the induction period.

The time to subject discontinuation in days for the induction period will be defined as the difference in days between the withdrawal date if occurring in the induction period and the date of first dose of study drug plus an additional day. The subject who will complete the induction period will be censored at the completion date of the induction period i.e. at the date of Week 12. For other subjects who did not withdraw during the induction period and did not complete the period, they will be censored at the date of the last known study visit during this period when they last received study treatment.

This graphical presentation and descriptive statistics will be repeated overall.

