## 7.0 DISCONTINUATION OF STUDY DRUG AND SUBJECT DISCONTINUATION/WITHDRAWAL

Subjects should be discontinued from study drug if any of the criteria described in Section 7.1 are met. Such subjects will continue to be followed for safety assessments as described in the SoA, Section 1.3, and Section 8.1.11.

Subjects may voluntarily withdraw from the study for any reason at any time, or be withdrawn by the investigator or the sponsor as per Section 7.2. The investigator should strongly recommend that withdrawn subjects return for follow-up visits approximately 28 days and 56 days after the last dose of study drug to assess their safety and, if willing, to assess duration of effect (e.g. rebound assessments). The information to be collected is identical to the Early Discontinuation visit, as described in the SoA (Section 1.3) and Section 8.1.11.

A subject will be considered lost to follow-up if he or she repeatedly fails to return for scheduled visits and is unable to be contacted by the study site. Such subjects will be considered to have discontinued the study.

Subjects who are prematurely discontinued from study treatment, or who have chosen to withdraw from the study, or who are lost to follow up, will not be replaced.

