  - Elevated transaminases (ALT or AST)  $>5 \times$  ULN without clear alternative etiology (tests should be repeated within 72 hours to verify the result prior to discontinuation.)
  - Any laboratory abnormalities that in the judgment of the investigator, taking into consideration the subject's overall status, prevents the subject from continuing participation in the study.
- Pregnancy (see Sections 8.5.5 and 10.4, Appendix 4).
- The subject develops a malignancy. (Exception: Subjects may be allowed to continue if they develop no more than 2 non-melanoma skin cancers (NMSC) during the study)
- Use of prohibited treatment as per recommendations in Section 6.5.
- Any other protocol deviation that results in a significant risk to the subject's safety.
- Administrative decision by the investigator, the sponsor or its designee to stop the subject's study treatment for medical, safety, regulatory, or other reasons consistent with applicable laws, regulations, and good clinical practice (GCP).
- Subject noncompliance (significant violation of protocol requirements or missing two consecutive visits).

In addition to these requirements for study treatment discontinuation, the investigator should discontinue study treatment for a given subject if, on balance, continuation would be detrimental to the subject's well-being. The investigator should carefully consider the subject's response at Week 24 and if there has been a worsening of psoriasis compared to baseline then the investigator should consider discontinuing the subject from the study if they are not receiving adequate benefit from their participation.

The appropriate personnel from the study site and the sponsor or its designee will assess whether study treatment should be discontinued for any subject whose treatment code has been broken inadvertently for any reason.

Subjects who discontinue study treatment should NOT be considered withdrawn from the study. They will continue to be followed up for assessments. See the SoA, Section 1.3 and Section 8.1.11 for the required assessments of these subjects after study treatment discontinuation.

Subjects should be considered to still be on study unless any of the criteria for study withdrawal are met (see Section 7.2).

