#### **8.1.11 Early Discontinuation**

The Early Discontinuation Visit involves two contacts with the subjects. The subject should attend the study site as close to possible to 4 weeks (28 days) after the last dose of study drug, and prior to the initiation of any other biological therapy. The reason for discontinuation should be discussed with the Medical Monitor. All subjects should then have further follow up either by telephone, or if they have ongoing SAEs or AEs, by attending the study site approximately 8 weeks (56 days) after the last dose of study drug to report any new, and follow up any existing AEs.

Patient reported outcomes (PRO) i.e. DLQI, EQ-PSO, SF-36, PHQ-8, and eC-SSRS should be performed before any other study procedures, assessments or consultations.

IGA, BSA and PASI should be conducted after the PROs and before other tests, procedures and consultations.

The following assessments will be performed and information collected:-

Visit 1 – As close as possible to 4 weeks (28 days) after the last dose of study drug, and prior to the initiation of any other biological therapy.

- DLQI
- EQ-PSO
- SF-36
- PHQ-8
- eC-SSRS
- IGA
- BSA
- PASI
- AEs
- Concomitant Medications
- Skin Evaluation
- Physical Examination
- Vital Signs
- Laboratory Analysis Chemistry and Haematology (Central Laboratory)
- Urinalysis (Local)
- Urine Pregnancy Test (Local)
- ECG (Standard 12 Lead, Central ECG Laboratory)
- Blood Sample for Immunogenicity – subjects testing positive may be requested to provide another sample six to twelve months after study completion
- Blood Sample for Pharmacokinetics

Visit 2 / Telephone Call – As close as possible to 8 weeks (56 days) after the last dose of study drug

- AEs
- Concomitant medication
- Male and female subjects of child bearing potential should be reminded that they must use highly effective contraception for a further 4 weeks

Following completion of the Early Discontinuation visits, subjects will continue to be contacted by telephone q4w as per the study schedule up to Week 52. The following information will be collected.

- AEs
- Concomitant medication
- Any new treatments for psoriasis

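### SAP 4.6.3 announces time to study drug discontinuation but defines time to subject discontinuation at an undefined withdrawal date, so on the protocol's meaning drug stops who stay in follow-up would be censored, not counted

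*SAP*

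**What the plan says.** The announced variable concerns the drug. SAP 4.6.1 lists "the time in weeks to study drug discontinuation due to any reasons and due to an AE for the induction period", and SAP 4.6.3 opens: "The time in weeks to study drug discontinuation due to any reasons and due to an AE will be represented graphically", by Kaplan-Meier, by treatment group, in the ITT population.

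The defined variable carries another name. The rule begins "The time to subject discontinuation in days for the induction period will be defined as"; what follows is a count of days with one added, and its two end points are given by the words "difference in days between the withdrawal date if occurring in the induction period and the date of first dose of study drug". Subjects who complete induction are censored at Week 12. For those who neither withdrew nor completed, "they will be censored at the date of the last known study visit during this period when they last received study treatment". The display is then repeated for the overall study. No separate event date is given for an AE-driven stop.

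The protocol keeps the two events apart. Its Section 7 is titled "DISCONTINUATION OF STUDY DRUG AND SUBJECT DISCONTINUATION/WITHDRAWAL", and 7.1 states: "Subjects who discontinue study treatment should NOT be considered withdrawn from the study". Under 8.1.11 a subject who stops drug has contacts about 28 and 56 days after the last dose, after which "subjects will continue to be contacted by telephone q4w as per the study schedule up to Week 52".

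**The concern.** The name of the curve and the rule that builds it point to different events. In this trial stopping drug does not end study participation, so the choice of event date decides who is counted.

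On the protocol's meaning of withdrawal, a subject who stops drug for an AE and then follows the protocol has no withdrawal date in induction. The last censoring rule would remove that subject at the last dosing visit, which is about when the event being plotted took place. That censoring is informative, and it would defeat the AE curve.

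Drug discontinuations are a named secondary safety endpoint (Protocol 3.0), and these curves are their time-based display in the only placebo-controlled period. Two programmers working from the same paragraph could also produce different curves.

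**Working it through.** The documents give no figure for these curves, so there is nothing to reproduce. The check sets the texts side by side and then illustrates the size with assumed counts.

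**1. What could withdrawal mean in SAP 4.6.3?**

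- *Study withdrawal.* The protocol's Section 7 title pairs subject discontinuation with withdrawal and sets both apart from stopping drug. SAP 4.6.3 uses these same two terms, subject discontinuation and withdrawal. The residual censoring group (neither withdrawn nor completed) also fits a drug stop still in follow-up; it would be nearly empty if withdrawal meant stopping treatment.
- *Treatment withdrawal.* SAP 4.1.1.3 applies the verb to treatment or study, 4.1.1.4 contrasts withdrawing with continuing to be treated, and 4.1.1.4.1 speaks of withdrawing treatment. The announced variable is about the drug.
- SAP 4.7.1 distinguishes a treatment discontinuation date from a study discontinuation date. Section 4.6.3 uses neither term.

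**2. How is a subject who stops drug for an AE in induction handled?**

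| Subject's course | Withdrawal = treatment | Withdrawal = study |
|---|---|---|
| Stays in follow-up | Event at drug stop | Censored at last dosing visit (or at Week 12 if classed as a completer) |
| Leaves the study later in induction | Event at drug stop | Event, but at the later exit date |

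**3. Size.** Input from the documents: about 50 subjects per arm (Protocol 9.2). Assumed: k AE-driven drug stops from about Day 28, of whom s leave the study from about Day 60, before Week 12; everyone else stays on drug to Week 12.

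- Event at drug stop: no censoring precedes the events, so incidence = k/50.
- Event at study withdrawal: the k − s who stay are censored first, leaving 50 − (k − s) at risk, so incidence = s / (50 − (k − s)).

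For k = 4:

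- correct value: 4/50 = 8%
- s = 0: 0/46 = 0%
- s = 2: 2/48 = 4.2%
- s = 4: 4/50 = 8%, with later event times

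Other counts:

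| k | Event at drug stop | Study reading, none leave | Study reading, half leave |
|---|---|---|---|
| 2 | 2/50 = 4% | 0% | 1/49 = 2.0% |
| 4 | 4/50 = 8% | 0% | 2/48 = 4.2% |
| 6 | 6/50 = 12% | 0% | 3/47 = 6.4% |
| 10 | 10/50 = 20% | 0% | 5/45 = 11.1% |

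If all k leave during induction, the Week 12 totals agree with the drug-stop column.

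**4. Would a study exit recorded at the 56-day contact rescue the count?** Contact week = last dose week + 8. Last doses at Weeks 0, 1, 2 and 3 give Weeks 8, 9, 10 and 11, inside induction. Last doses at Weeks 4, 6, 8 and 10 give Weeks 12, 14, 16 and 18, at or after its end. So it would help only for the earliest stops, and then with a delay of about eight weeks from the last dose.

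**The case against.** The strongest objection is that the SAP never defines the withdrawal date, and its missing-data sections use the word for treatment as well as study. Since both 4.6.1 and 4.6.3 name the variable as drug discontinuation, a programmer could reasonably take the event to be withdrawal of drug, and every stop is then counted. This stands. A reader might infer that the plan definitely censors AE-driven stops; the documents do not support that, only that one of two available readings does so.

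A reader might also infer that no drug stop could ever be an event on the study reading. That goes too far. Protocol 7.1 lists withdrawal of consent among the reasons for stopping drug, and 7.2 lets subjects leave at any time. Those who leave in induction are counted, though possibly late. A contrast of 8% with 0% is therefore the extreme of an assumed range.

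Finally, AE-driven stops are reported elsewhere. SAP 4.9.2.5 plans overview and incidence tables of TEAEs leading to discontinuation, and 4.6.1 tabulates discontinuations with primary reason by period. The tolerability information is not lost. What remains is that the curves could disagree with those tables, and that the reading closest to the protocol's terms gives the wrong curve.

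**Conclusion.** The point holds as a mismatch between the announced and the defined variable, made material by an undefined event date. On the protocol's meaning of withdrawal, drug stops who stay in follow-up are censored at about the time of their event, and those who leave later in induction are counted late. On the treatment meaning they are counted correctly.

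The size depends on assumed counts: for 4 AE stops in 50, a displayed Week 12 incidence between 0% and 8%, about 4% if half leave the study, against a correct 8%.

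The effect is confined to descriptive disposition curves, in induction and in the overall repeat. The primary analysis, the power, and the tables of discontinuations by reason and of TEAEs leading to discontinuation do not change. It should be corrected because the paragraph states a rule that can produce a wrong curve for a named safety endpoint.

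**What to change.** Rewrite the definition in SAP 4.6.3 as follows.

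- **Event date:** the date of permanent study drug discontinuation, whether or not the subject stays in the study, with the last dose date if it is missing. Apply one rule to all arms: SAP 4.7.1 uses a treatment discontinuation date for placebo subjects but builds on the last dose date for the active arms.
- **Censoring:** subjects still on drug at the Week 12 visit are censored there. Subjects lost to follow-up with no known stop date are censored at their last dosing visit.
- **AE curve:** count only stops with an AE as the recorded primary reason. State whether non-AE stops are censored at the stop date or treated as competing events.
- **Study withdrawal:** if wanted, define it as a separate variable under its own name.
- **Overall repeat:** apply the same definitions.

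The cost is about one paragraph. The SAP already relies on a treatment discontinuation date (4.7.1) and on treatment discontinuation by primary reason for the later periods (4.6.1), so no new data should be needed. The documents do not say expressly that the eCRF holds a drug-stop date and reason for every induction stop, so this should be confirmed. The small downside is that displayed discontinuation rates may look less favourable.
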